#### 2.1.4 Analysis of safety parameters

The descriptive part of the safety analysis will include an assessment of frequencies and bilateral 95% CIs for the following indicators in each treatment group:

- AE: the overall frequency and frequency of individual categories in general within the study and in groups;
- SAE: the overall frequency and frequency of individual categories in general within the study and in groups;
- the frequency of clinically significant changes in the results of physical examination by visits and groups;
- the frequency of clinically significant changes in laboratory parameters by visits and groups;
- the frequency of clinically significant changes in the indices of the main parameters of vital activity (body temperature, blood pressure, heart rate, respiration rate) by visits and groups;
- Comprehensive assessment of the tolerability of treatment by the researching doctor and the patient (assessment of the frequency for each response category);

Comparison of frequencies between treatment groups will be carried out using the  $\chi^2$  criterion; the relative risk index will additionally be calculated. Evaluation of the dynamics in the course of the study ("before-after") for all re-studied frequencies will be conducted within each group using the McNemar criterion or Madansky criterion.

In addition to frequency indicators, the tabular form will show the values of all quantitative indicators of safety (laboratory data, vital signs) by visits and groups. The decision to conduct a statistical analysis of the specified data on visits and groups will be made at the stage of finalizing the plan for statistical data analysis.

The analysis of safety parameters will be carried out in the safety population (safety).

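### SAP 2.1.4 compares examination, laboratory and vital-sign changes between arms by visit, with no count of patients ever affected; adding one is a cheap, minor improvement

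*SAP*

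**What the plan says.** SAP 2.1.4 lists the safety frequencies to be reported. Adverse events are counted over the whole study: "AE: the overall frequency and frequency of individual categories in general within the study and in groups". Serious adverse events have the same wording. The three measures of clinically significant change are listed differently:

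- examination: "the frequency of clinically significant changes in the results of physical examination by visits and groups";
- laboratory: "the frequency of clinically significant changes in laboratory parameters by visits and groups";
- vital signs, in an item that ends "heart rate, respiration rate) by visits and groups".

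The section then says "Comparison of frequencies between treatment groups will be carried out" by chi-square, and "the relative risk index will additionally be calculated". Before-after tests are planned within each arm only. One testing decision is postponed: "The decision to conduct a statistical analysis of the specified data on visits and groups" is left until the analysis plan is finalised, and it concerns the quantitative laboratory and vital-sign values, not these frequencies.

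Under SAP 2.6, missing safety data are not imputed. The Protocol synopsis schedules joint examination and vital signs at Visits 2 to 5 after the first injection, and the laboratory panel at Visits 3 to 5. Unscheduled visits record joint examination and vital signs. The premature discontinuation visit repeats the Visit 5 procedures.

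**The concern.** A harm that appears once and resolves, or after which the patient leaves, shows in only one visit table. If such findings are spread over the follow-up, each table holds only part of the difference between arms, and no planned comparison of these three measures puts the parts together.

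The Protocol makes this pattern foreseeable. Subject exclusion criterion 9 removes a patient who meets a non-inclusion criterion during the study. Those criteria include abnormal coagulation results, an abnormal platelet count, leukocytosis or raised ESR, uric acid above 360 μmol/l, and liver values above three times the upper limit. The safety drop-out rate in SAP 2.1.3 counts exclusion criteria 2, 3, 6 and 7, so it does not count a removal recorded under criterion 9. The supplied text also does not say which visit table receives a finding from an unscheduled or discontinuation visit.

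At stake is a report of no significant difference at any visit although the proportions of patients ever affected differ. Several unadjusted visit tests can also raise a false alarm, but this is secondary.

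**Working it through.** **Inputs.** SAP 2.3 gives 72 randomised per arm; SAP 2.1 and 2.4 give two-sided tests at 5%. The plan states no figure for the safety comparisons. Its only power figure is for the primary endpoint and reproduces: at N = 128, λ = 128 × 0.25² = 8.0, denominator df = 128 − 2 − 2 = 124, power 0.801. The SAP rounds this to 130 completers and 144 randomised. This does not bear on the point beyond supplying 72 per arm.

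**Number of comparisons.** Examination 4 visits + vital signs 4 visits + laboratory 3 visits = at least 11 by-visit comparisons, against 3 any-time comparisons if each measure is counted once.

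**Power.** The any-time risks (10%, 15% or 20% on the device against 3% on placebo) are assumptions. The test is Pearson chi-square without continuity correction, counted when p < 0.05 with the device arm higher; 200,000 simulated trials per scenario. By-visit testing is credited with success if any single unadjusted visit is significant, which favours it.

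| Scenario | 10% v 3% | 15% v 3% | 20% v 3% |
|---|---|---|---|
| Any-time count | 41% | 76% | 94% |
| 3 visits, even spread, patient leaves | 31% | 64% | 86% |
| 4 visits, even spread, patient leaves | 23% | 55% | 81% |
| 3 visits, 80/10/10% spread, patient leaves | 33% | 67% | 88% |
| 4 visits, 80/10/5/5% spread, patient leaves | 33% | 66% | 88% |
| 3 visits, even spread, transient, patient stays | 30% | 61% | 83% |
| 4 visits, even spread, transient, patient stays | 23% | 54% | 78% |
| 3 visits, finding persists | 47% | 80% | 95% |

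Where the patient leaves and findings are evenly spread, the loss is 8 to 13 points over three visits and 13 to 21 over four. With 80% of findings at one visit it is about 6 to 10 points. The transient, patient-stays rows are up to 3 points lower than the corresponding rows where the patient leaves, with a largest loss of 76 − 54 = 22 points. If the finding persists, the Visit 5 test alone has the any-time power, so nothing is lost.

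**Illustration at 15% v 3%.** Expected counts are 72 × 0.15 = 10.8 and 72 × 0.03 = 2.2, so take 11 and 2.

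- Any-time: χ² = 144 × (11×70 − 2×61)² / (13 × 131 × 72 × 72) = 6.85, p = 0.009. Relative risk = 11/2 = 5.5. SE of its log = √(1/11 − 1/72 + 1/2 − 1/72) = 0.750, so the 95% CI is 1.3 to 23.9.
- Split over three laboratory visits as 4, 4, 3 against 1, 1, 0, with 72 as denominator: p = 0.17, 0.17 and 0.08.
- At 10% v 3% (7 against 2), the any-time test is not significant either (p = 0.085).

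**False alarms.** With equal any-time risk in both arms and transient findings, the chance of at least one significant visit is 13–14% at a risk of 10%, 4–6% at 5% and 1–2% at 3%. The any-time test gives 5%, 5% and 4%.

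**Pooling check.** Suppose the real difference is in one laboratory parameter (15% v 3%), and the other parameters add an assumed independent 15% background in each arm. A pooled laboratory count then compares 1 − 0.85 × 0.85 = 27.8% with 1 − 0.85 × 0.97 = 17.5%. Its power is 32%, against 76% for the single parameter counted any-time and 64% for three by-visit tests of that parameter.

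**The case against.** The by-visit wording stands in a list introduced as descriptive, and the sentence on testing does not say that tests are confined to single visits. SAP 2.1 calls the section a brief outline and leaves the full analysis to a later plan. This is fair as far as it goes: a reader might infer that the SAP rules out an any-time comparison, and it does not. But it names the test and the by-visit grouping and supplies no any-time count, so someone following it would produce by-visit tests.

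A reader might also infer that the trial would be blind to this kind of harm. The documents do not support that. Whole-study adverse-event and serious-adverse-event frequencies are compared between arms. Exclusion criterion 7 names active arthritis and hemarthrosis of the target knee as adverse events, so the most relevant joint findings are covered. "Comprehensive assessment of the tolerability of treatment by the researching doctor and the patient" is also compared, and the safety drop-out rate is a per-patient count over the whole study. The cover is incomplete: removals under criterion 9 are outside that drop-out rate, and the supplied text has no rule that a clinically significant abnormality must be reported as an adverse event. If there is such a rule, the gap is smaller.

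The remaining objections concern size and remedy. The loss depends on assumed rates and on clustering, and for persistent findings the by-visit tests do slightly better. The false-alarm argument is weak: figures of 14% or 19% for three or four tests assume independent tests that each have exactly 5% size, which sparse counts do not have. And one pooled proportion per measure could be worse than what is planned, as the pooling check shows. All of this stands and shapes the fix.

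**Conclusion.** The point holds as a minor one. For transient findings, or findings after which the patient leaves, by-visit comparison costs about 6 to 21 points of power (22 in the worst transient scenario), under assumed any-time risks of 10–20% against 3% with 72 per arm. The loss is nil if findings persist to Visit 5 or all fall at one visit. At 10% v 3% neither approach has useful power. False alarms clearly exceed 5% only when findings are common in both arms (13–14% at an any-time risk of 10%).

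It would be wrong to conclude that the safety analysis is unsound. A conclusion on safety would not rest on these three sets of tables alone, and neither the primary analysis nor the sample size is affected.

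**What to change.** In SAP 2.1.4, before database lock:

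- For each laboratory parameter, each vital sign and the joint examination, add the number and proportion of safety-population patients with at least one clinically significant change at any time after injection 1. Count scheduled, unscheduled and discontinuation visits, with all treated patients in the arm as denominator.
- Base the between-arm chi-square and the relative risk, with 95% CI, on this count. Give a pooled row per measure as a summary only.
- Keep the by-visit tables as descriptive, with the number examined at each visit.
- Report beside it a version limited to scheduled visits and the number of off-schedule examinations per arm.

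The cost is SAP wording and a few table rows; no new data are needed. The downside is possible unequal ascertainment: the arm with more complaints may be examined more often off schedule and so show a higher any-time count. The scheduled-only version and the examination counts show whether that matters.

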	- 130 patients that should complete the study (65 patients in each group).			
Study aim	The aim of this double-blinded controlled study is to assess clinical			
	efficacy and safety of intra-articular polyacrylamide hydrogel with ions			
	of silver in comparison with placebo (0.9% sodium chloride solution) in Kellgren Lawrence radiological grade II-III knee osteoarthritis			
	Religion Lawrence radiological grade 11-111 knee osteoaruntus			
Study goals	Assessment of a change in knee joint functionality, stifnes and			
	joint pain intensity estimated per the corresponding subscales			
	and total arthritis index score developed by Western Ontario			
	and McMaster Universities (WOMAC) during administration of			
	intra-articular MD NOLTREX TM in comparison with placebo			

(0.9% sodium chloride solution) in Kellgren Lawrence radiological grade II-III knee osteoarthritis;

- Assessment of the need in paracetamol and NSAID (in case of ineffective therapy with paracetamol) intake to relieve the knee pain during administration of intra-articular MD NOLTREXTM in comparison with placebo (0.9% sodium chloride solution) in Kellgren Lawrence radiological grade II-III knee osteoarthritis;
- Assessment of efficacy of MD NOLTREXTM in comparison with placebo (0.9% sodium chloride solution) in Kellgren Lawrence radiological grade II-III knee osteoarthritis as subjectively assessed by a patient;
- Assessment of efficacy of MD NOLTREXTM in comparison with placebo (0.9% sodium chloride solution) in Kellgren Lawrence radiological grade II-III knee osteoarthritis as subjectively assessed by the investigator;
- Assessment of **safety** of intra-articular MD NOLTREX[™] in comparison with placebo (0.9% sodium chloride solution) in Kellgren Lawrence radiological grade II-III knee osteoarthritis.

Study methodology

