- 30) Severe decompensated chronic or acute diseases and other conditions which, by the opinion of the study physician, may preclude the patient's participation in the study or affect the study results.

Subject exclusion criteria

- Ethics Committee, regulatory bodies or the Sponsor terminate the study or participation of the clinical site in the study for any reasons;
 - Need in paracetamol or NSAID intake due to knee osteoarthritis 4 days a week or more during 2 successive weeks;
 - 3) The investigator makes the decision that a patient should discontinue the study in the best interests of the patient;
 - Informed consent revocation (patient's unwillingness to continue the study);
 - 5) Major deviation from the study protocol;
 - Individual intolerability or contraindications to the study MD, placebo or paracetamol;
 - AE/SAE which requires examination and/or treatment affecting significantly the study procedures (in particular, development of active arthritis or hemarthrosis of the target knee joint);

- 8) Erroneous study inclusion (for example, the patient was included with a violation of the protocol inclusion/non-inclusion criteria);
- 9) A patient has non-inclusion criteria during the study;
- 10) A patient takes/needs additional treatment which can affect the study result or patient's safety (see section "Disallowed concomitant therapy");
- 11) Other conditions or events which require, by the opinion of the study physician, the patient's exclusion from the study.
- 12) Injury of the studied joint.

Disallowed concomitant therapy

- 1. Glucocorticosteroids in any dosage form;
- 2. Any intra-articular or peri-articular injections, physical therapy, as well other therapeutic or rehabilitation measures for knee osteoarthritis, except the study procedures;
- NSAIDs and analgesics including the local ones (except for paracetamol and NSAIDs permitted by the protocol in cases when paracetamol is ineffective);
- 4. Paracetamol intake in dose over 4000 mg a day;
- 5. the use of one of the NSAIDs permitted by the Protocol in doses exceeding those permitted by the Protocol (permitted drugs and doses: diclofenac potassium 50 mg 2 times a day, diclofenac sodium tablets 75 mg 2 times a day, naproxen tablets 500 mg 2 times a day, naproxen sodium tablets 550 mg 2 times a day, meloxicam tablets 7.5 mg once a day, celecoxib tablets 200 mg 2 times a day);
- use of NSAID in combination with paracetamol or combination of two or more NSAID;

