## 2.4 Applicable level of significance

For all parameters of efficacy, safety and tolerability the bilateral statistical criteria will be used at a 95% significance level (the threshold value p for confirming statistical significance is less than 0.05).

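### The safety comparison between arms rests on a chi-square test and a relative risk without an interval; adding a risk difference with a 95% CI would show what excess harm the data cannot exclude

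*SAP*

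**What the plan says.** The Protocol Synopsis gives the aim in the sentence that begins "The aim of this double-blinded controlled study is to assess clinical" and goes on to name efficacy and safety in comparison with placebo. Safety against placebo is also listed among the study goals.

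SAP 2.1.4 has two layers. The descriptive layer is "an assessment of frequencies and bilateral 95% CIs for the following indicators in each treatment group". It covers adverse events, serious adverse events, clinically significant changes (physical examination, laboratory, vital signs) and tolerability. The comparative layer is: "Comparison of frequencies between treatment groups will be carried out using the $\chi^2$ criterion; the relative risk index will additionally be calculated". No interval is mentioned for the relative risk, and a risk difference is not mentioned at all.

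SAP 2.4 covers efficacy, safety and tolerability together: "the bilateral statistical criteria will be used at a 95% significance level", where "the threshold value p for confirming statistical significance is less than 0.05".

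SAP 2.3 derives the sample size from WOMAC-T only. SAP 2.8.3 makes the safety set the same patients as the ITT set, analysed by the device actually received, so there are about 72 patients per arm at most.

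**The concern.** A comparison of safety with placebo asks how much more often an event happens on the device, and how large that excess could be given the data. A within-arm interval does not answer this directly, a relative risk without an interval gives no idea of its precision, and a p-value answers a different question.

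The gap matters most for infrequent events. Protocol exclusion criterion 7 gives examples: "in particular, development of active arthritis or hemarthrosis of the target knee joint". If such events are few, three things can happen under the plan as written:

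- a several-fold excess is reported as not significant, with no interval beside it to show what remains possible;
- the relative risk cannot be computed, because placebo has no events;
- the p-value depends on which test is used, because the chi-square approximation is poor in sparse cells and no alternative is named.

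At stake is how clearly the report answers the safety half of the aim.

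**Working it through.** **Inputs from the documents.** Two-sided alpha 0.05 (SAP 2.4); chi-square test (SAP 2.1.4); 144 randomized, 72 per arm, and 130 completers, 65 per arm (SAP 2.3).

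**Inputs assumed.** Event rates in each arm. The documents give none, so a range is shown.

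**Step 1: the plan's own figure.** For the efficacy ANCOVA, the noncentrality is f² × N and the denominator df is N − groups − covariates. With f = 0.25 and N = 128, this gives 0.0625 × 128 = 8.0 and 128 − 2 − 2 = 124. The critical F is 3.9175 and the power 0.8014, which matches the printed output; 130 is that N rounded up. The calculation concerns WOMAC-T, and there is no counterpart for safety.

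**Step 2: power of the planned safety test.** For x₁ and x₂ events in 72 and 72 patients, X² = (p₁ − p₂)² / [p̄(1 − p̄)(2/72)], without continuity correction, significant if X² > 3.841. All 73 × 73 possible tables were enumerated and the binomial probabilities of the significant ones summed.

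| Device vs placebo (assumed) | Power, 72 per arm | Power, 65 per arm |
|---|---|---|
| 5% vs 0% | 49% | 41% |
| 6% vs 2% | 21% | 19% |
| 10% vs 5% | 21% | 19% |
| 15% vs 5% | 54% | 49% |
| 20% vs 10% | 39% | 35% |
| 20% vs 5% | 81% | 77% |
| 30% vs 10% | 87% | 83% |

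Excesses of about 5 points, and doublings from a placebo rate of 10% or less, are missed more often than found. The excess needed for 80% power is about 10 points at a 1% placebo rate, 15 at 5%, 18 at 10% and 21 at 20%.

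**Step 3: what an interval would add.** The Newcombe limits combine the Wilson limits (l, u) of each arm: lower = d − √[(p₁ − l₁)² + (u₂ − p₂)²]; upper = d + √[(u₁ − p₁)² + (p₂ − l₂)²].

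Worked case, 6/72 vs 1/72, in percentage points: p₁ = 8.33 (3.88 to 17.01), p₂ = 1.39 (0.25 to 7.46), d = 6.94.

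- Lower: 6.94 − √(4.46² + 6.07²) = 6.94 − 7.53 = −0.6.
- Upper: 6.94 + √(8.68² + 1.14²) = 6.94 + 8.75 = +15.7.

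| Events, device vs placebo | Chi-square p | Relative risk (95% CI, log method) | Risk difference, points (95% CI) |
|---|---|---|---|
| 3 vs 0 | 0.080 | undefined | 4.2 (−1.6 to 11.5) |
| 6 vs 1 | 0.053 | 6.0 (0.74 to 48.6) | 6.9 (−0.6 to 15.7) |
| 8 vs 4 | 0.23 | 2.0 (0.63 to 6.35) | 5.6 (−4.0 to 15.5) |
| 14 vs 7 | 0.098 | 2.0 (0.86 to 4.66) | 9.7 (−2.0 to 21.4) |

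Under the plan, each row would show the p-value and, where defined, the relative risk alone. The last column and the relative risk limits would be absent.

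**Step 4: sparse cells.** For 4/72 vs 0/72, p̄ = 4/144 = 0.0278 and X² = 0.0556² / (0.0278 × 0.9722 × 2/72) = 4.11, so p = 0.043. Fisher's exact test gives 0.12. The expected number of events is only 2 per arm. For 8 vs 2 the two tests give 0.049 and 0.097.

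**The case against.** **The plan never equates non-significance with safety.** This is correct. A reader might infer from 2.4 that p>=0.05 would count as comparable safety, but that section only says when significance is declared. No equivalence or non-inferiority claim on safety is planned, so the absence of a margin is not a defect.

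**The p-value is not the only safety information.** Also correct. Within-arm intervals and the relative risk are planned. The Protocol asks for severity, duration, relationship and outcome of each event. Exclusion for safety reasons is a secondary endpoint, and SAP 2.5 allows the study to be stopped on the frequency or severity of adverse events without any p-value. With no placebo events, the Newcombe upper limit equals the device arm's own Wilson upper limit (11.5% for 3 of 72), which the planned within-arm CI would show if that method is used. A reader could also compute the difference interval from the counts. What stands is that the reader would have to do so, because the report would not contain it.

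**Low power comes from the sample size.** True. An interval changes none of the powers above, and a trial sized for efficacy is usually weak on uncommon events.

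**The uncorrected chi-square flags more than Fisher's test.** True for 4 vs 0 and for 7 vs 1 (0.029 against 0.063). The test is therefore not lenient towards harm. The point is that the result turns on the choice of test.

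**Detail is deferred.** SAP 2.1 calls itself a brief description and leaves the full analysis to a later plan, which might contain the interval. That plan is not among the documents. The explicit deferral within 2.1.4 concerns quantitative laboratory and vital-sign values, not the comparison of frequencies.

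**Conclusion.** The point holds as a reporting gap. The planned between-arm safety output is a chi-square p-value and a relative risk without an interval, and nothing planned directly bounds the excess risk over placebo. At 72 per arm and under assumed rates, a non-significant result is weak evidence about moderate or infrequent harms: power is 21% for 10% against 5%, and 39% for 20% against 10%.

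A reader might go further and conclude that most relevant excess harms would be missed. The documents do not support that. They define no relevant excess and give no event rates, and large excesses are usually detected (81% and 87% in the two largest scenarios). Nor do they show that placebo will have no events; that is a possibility for rare reactions, not a stated expectation.

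The powers rest on the assumed rates, on full 72 per arm and on the uncorrected test. The absence of a between-arm interval rests on the text alone. This is a cheap improvement of minor priority.

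**What to change.** In SAP 2.1.4:

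- make the main between-arm safety summary the risk difference (device minus placebo) with a two-sided 95% CI, by the Newcombe or Miettinen-Nurminen method, for each frequency already listed;
- add a 95% CI to the planned relative risk where both arms have events, and say that it is not estimated otherwise;
- treat any p-value as descriptive, with Fisher's exact test for sparse cells.

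In SAP 2.4, state that p>=0.05 on a safety frequency is not evidence of comparable safety.

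The cost is a few sentences and an interval or two per table row, with no new data or patients. Power does not change; the gain is that the report shows which excesses the data cannot exclude. The small downside is that many intervals will be wide and the report will have less scope to claim comparable safety.

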- 3) Varus or valgus deformation of the target knee joint;
- 4) Instability of the target knee joint;
- 5) Active inflammation of the target knee joint (edema, hyperemia, present effusion) at the study entry;
- 6) Microcrystalline arthropathies;
- 7) Systemic inflammatory disease (rheumatoid arthritis, systemic lupus erythematosus, etc.);
- 8) Seronegative spondiloarthritis and reactive arthritis;
- Inflammatory diseases of the skin and soft tissues in the proposed injection site for the study MD or placebo in the target joint;
- 10) History of venous thrombosis and thromboembolias;
- 11) Coagulogram abnormalities (APTT, prothrombin time, prothrombin index, fibrinogen);
- 12) Inflammatory changes in the complete blood count (leukocytosis, increase of erythrocyte sedimentation rate [ESR]);
- 13) Platelet count abnormality (in accordance with the reference ranges of the local laboratory;
- 14) Increase of rheumatoid factor level;
- 15) Increase of uric acid level > 360 μmol/l;
- 16) Diabetes mellitus:
- 17) Hemophilia and other hemorrhagic diatheses, as well administration of anticoagulants and disaggregants;
- 18) Positive results of HIV, HBs-Ag, anti-HCV, RW tests;
- 19) Intra-articular injection to the target knee joint:
 - MD NOLTREXTM within 24 months prior patient's inclusion to the study;
 - hyaluronates within 6 months prior patient's inclusion to the study;
 - glucocorticosteroids within 1 month prior the study inclusion;
 - non-steroidal anti-inflammatory drugs (NSAID) within 3 weeks prior patient's inclusion to the study.

- 20) Oral administration of non-steroidal anti-inflammatory drugs (NSAID) within 2 weeks prior the study inclusion;
- 21) Necessity of systemic glucocorticosteroids intake in any dosage form;
- 22) Paracetamol administration within 48 hours prior the study inclusion;
- 23) Pregnancy and lactation;
- 24) Hypersensitivity to components of the study MD or placebo;
- 25) Severe liver disorder determined as the increase of one of the values: ALT, AST, ALP, total bilirubin, GGTP more than 3 times the upper limit of normal;
- 26) Renal diseases with the glomerular filtration rate estimated per Cockraft-Gault formula less than 60 ml/min/1.73 m² (III-V stage chronic renal disease [CRD]);
- 27) Clinically manifested hip osteoarthritis;
- 28) History of knee and coxofemoral endoprosthesis;
- 29) Acute infectious diseases or infectious aggravations of chronic diseases (respiratory infections) within one month prior the study inclusion;

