A priori: Compute required sample size Analysis: Input: Effect size f = 0.25= 0.05α err prob Power (1–β err prob) = 0.80= 1 Numerator df Number of groups = 2 Number of covariates = 2 = 8.0000000 Output: Noncentrality parameter  $\lambda$ Critical F = 3.9175498Denominator df = 124 = 130 Total sample size Actual power = 0.8013621

In this case, taking into account rounding, the study should complete 130 patients (65 in each group), for which it is necessary to randomize 144 patients (72 in each group).

Accordingly, to achieve the required number of randomized patients, it is necessary to screen up to 170 patients.

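### Within-arm McNemar/Madansky safety tests (SAP 2.1.4) can turn significant in either arm with no device effect, for findings that the entry criteria exclude at baseline

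*SAP*

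**What the plan says.** SAP 2.1.4 lists the safety frequencies to be reported, among them "the frequency of clinically significant changes in laboratory parameters by visits and groups", with matching items for physical examination and vital signs. It plans two kinds of test:

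- **Between arms:** "Comparison of frequencies between treatment groups will be carried out using the" chi-square criterion, with relative risk in addition.
- **Within arms:** before-after evaluation "for all re-studied frequencies will be conducted within each group using the McNemar criterion or Madansky criterion". The version of McNemar (exact, uncorrected or continuity-corrected) is not given, nor is it said when Madansky would replace it. The section defers only the decision on analysing the quantitative safety values; it does not defer these tests.

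SAP 2.4 covers safety as well as efficacy: "bilateral statistical criteria will be used", and "the threshold value p for confirming statistical significance is less than 0.05". No multiplicity adjustment is stated.

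The Protocol's non-inclusion criteria bar, among others, "Coagulogram abnormalities (APTT, prothrombin time, prothrombin index, fibrinogen" (criterion 11) and "Active inflammation of the target knee joint (edema, hyperemia, present effusion) at the study entry" (criterion 5). Criteria 12, 13 and 15 bar leukocytosis or raised ESR, an abnormal platelet count, and uric acid above 360 μmol/l. Blood count, biochemistry and coagulogram are taken at screening, are not listed at Visit 1, and are repeated at Visits 3, 4 and 5. The joints are examined at every visit.

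**The concern.** McNemar's test asks whether changes from normal to abnormal are as frequent as changes from abnormal to normal. For a parameter screened at entry, the second kind of change cannot occur, because nobody enters abnormal (patients enrolled in error aside). For the laboratory tests the position is plain: the only value before treatment is the screening value that admitted the patient. The null hypothesis is therefore false from the start in both arms, and ordinary biological variation and regression to the mean count as deterioration. The placebo arm, which would remove this, plays no part in a within-arm test.

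What is at stake is how the safety report reads. It would carry two sets of p-values for the same findings, and they can disagree. The most misleading result is a split: significant on one arm and not on the other, with no true difference. That could be taken as a device effect or as reassurance, depending on which arm crossed the line.

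**Working it through.** **Plan's own figure.** The documents give none for this analysis. The one figure taken over is the arm size in SAP 2.3: "it is necessary to randomize 144 patients (72 in each group". With the stated 10% drop-out, 144 × 0.9 = 129.6, in line with the 130 completers (65 per arm) in the same section.

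**Assumed inputs.** The documents give no rate of new findings. Rates π of 1%, 2%, 5% and 10% per parameter are taken as a range, equal in both arms (no device effect). The arms are independent.

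**Step 1: threshold for significance.** Let b be abnormal-to-normal pairs and c normal-to-abnormal pairs. Selection gives b = 0, so:

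- Uncorrected: chi-square = (b − c)²/(b + c) = c. At c = 3, p = 0.083; at c = 4, p = 0.0455. Four new findings suffice (4/72 = 5.6%).
- Exact: p = 2 × 0.5^c. At c = 5, p = 0.0625; at c = 6, p = 0.031. Six suffice (6/72 = 8.3%).
- Continuity-corrected: chi-square = (c − 1)²/c. At c = 5, p = 0.074; at c = 6, p = 0.041. Again six.

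**Step 2: chance of significance.** With C ~ Binomial(72, π), P = P(C ≥ 4) uncorrected or P(C ≥ 6) exact. Both arms: P². Exactly one arm: 2P(1 − P). For example, at 5% exact: P = 0.1509, P² = 0.023, 2 × 0.1509 × 0.8491 = 0.256.

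| Assumed rate | Uncorrected: given arm / both / only one | Exact: given arm / both / only one |
|---|---|---|
| 1% | 0.6% / <0.1% / 1.2% | <0.1% / <0.1% / <0.1% |
| 2% | 6% / 0.3% / 11% | 0.3% / <0.1% / 0.6% |
| 5% | 49% / 24% / 50% | 15% / 2% / 26% |
| 10% | 94% / 88% / 12% | 74% / 54% / 39% |

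These are for one parameter at one visit; the plan tests several at up to three visits.

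**Step 3: completers only (65 per arm).** For a given arm the figures are 41% (uncorrected) and 11% (exact) at 5%, and 90% and 64% at 10%. Only one arm significant at 5%: 2 × 0.4100 × 0.5900 = 48%, and 2 × 0.1059 × 0.8941 = 19%.

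**Step 4: is selection the cause?** With 72 pairs and discordance free to go either way with equal chance, McNemar's type I error at total discordance of 5% and 10% is 3.8% and 4.6% (uncorrected) or 0.4% and 1.6% (exact). The excess in Step 2 comes from the empty cell.

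**Step 5: the planned between-arm test.** The exact type I error of the chi-square at 72 per arm, with equal rates of 1%, 2%, 5% and 10%, is 0.006, 0.027, 0.048 and 0.051. Entry selection acts alike on both arms and does not inflate it.

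**Step 6: scope.** Non-inclusion criteria set against the repeated measurements:

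- Affected: coagulogram, leukocytes/ESR, platelets, uric acid, target-knee inflammation.
- Liver tests: affected only above 3 × ULN (criterion 25); values of 1–3 × ULN may be present at entry.
- No entry threshold: vital signs, urinalysis, glucose (diabetes is barred, but no glucose limit is set).
- Rheumatoid factor (criterion 14) is not repeated, so no before-after pair exists.

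**The case against.** **The rates are assumed, and the indicator may be rare.** The SAP counts clinically significant changes, not every value out of range. At 1–2% the exact test is almost never significant. This stands, and it limits the size of the point. The uncorrected version, which the SAP does not rule out, still gives 6% for a given arm at 2%.

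**Later counts may be lower still.** Subject exclusion criterion 9 removes patients who develop a non-inclusion criterion, and SAP 2.6 provides no imputation for safety data. This stands in part: the premature discontinuation visit repeats the Visit 5 procedures, so such findings need not be lost.

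**A sound comparison is already planned.** The between-arm chi-square and relative risk stand next to the within-arm tests in 2.1.4, and no stopping reason in SAP 2.5 refers to a within-arm p-value. This stands and limits the harm. It also makes the within-arm tests redundant, since for the screened parameters they add only a p-value that does not isolate the device.

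**Two stronger readings are tempting.** A reader might infer that both arms will show significant worsening. The documents do not support that. It depends on rates and a test version that they do not give; at 5%, both arms are significant in only 24% (uncorrected) or 2% (exact) of trials. A reader might also infer that every safety frequency is affected. The scope list shows otherwise. It is true that a clinically significant change has no obvious state before treatment, so the before-after table is poorly defined for those items, but that is a gap in definition and not a bias from selection.

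**Conclusion.** The point holds for the repeated parameters screened at entry. For these, the within-arm test can only point to worsening, and its nominal 5% level says nothing about a device effect. Either arm can become significant under no effect, with a chance that runs from negligible at a 1% rate to 74% (exact) or 94% (uncorrected) at 10%. A split between arms is most troublesome at middling rates: 26% or 50% at 5%.

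The size rests on assumed rates equal in both arms, on 72 evaluable patients per arm and on McNemar. Madansky was not computed, but any before-after comparison within one arm meets the same empty cell. The primary endpoint is untouched and the between-arm safety comparison is sound. The change should be made because the affected p-values are open to misreading and cost little to remove.

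**What to change.** In SAP 2.1.4, remove the within-arm McNemar/Madansky p-values. If before-after results are wanted, present them as descriptive shift tables by arm and visit, without tests, with the normal and abnormal states defined for each parameter. State that safety inference rests on the between-arm comparison of new post-baseline findings, using the chi-square and relative risk already planned, and give the relative risk with a 95% CI.

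Cost: SAP wording and a table shell, with no new data or visits. SAP 2.1 says that the full analysis is still to be described, so there is room for it. What is lost is a set of within-arm p-values that do not isolate a device effect.
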